9.2 Study Procedures

Please see study schema (Appendix C) for study flow.

Pre-Transfusion

- Once identified by Epic scheduling report, provider suggestion, or study-specific Epic Workbench report, eligible patients will be approached for consent discussion at an appointment with their provider.
 - Patients with Hb approaching 8.5 g/dL will be approached at an appointment prior to an upcoming transfusion.
 - Patients that are transfusion-dependent will be approached at an upcoming appointment with their provider or during a transfusion appointment.
- During this initial encounter, consenting participants will be given a study packet containing a paper copy of the QUALMS. Study participants will be instructed to fill out the survey on the day before their upcoming pRBC transfusion.

**PROTOCOL TITLE: A New Paradigm of Transfusion Decision Support for Patients with MDS:
Using Peri-Transfusion Quality of Life Assessments (PTQAs)**

3. Study participants will indicate whether they would like to receive PTQA reports in person, via mail, or via email.
4. Site RAs will call study participants using script (see Appendix D) on the day prior to an upcoming transfusion to remind them to complete the QUALMS and bring it with them to their transfusion.
5. Note: Index transfusion is defined as any upcoming transfusion appointment for which the participant has completed both the pre- and post-transfusion QUALMS questionnaires.
 - If a participant does not complete the pre-transfusion questionnaire for any reason (i.e., participant forgot to complete at home or forgot to bring in), then the RA may ask the participant to complete the questionnaire at home prior to a subsequent transfusion appointment. This subsequent transfusion will become the index transfusion.
 - If a participant does not complete the pre-transfusion QUALMS at home prior to the appointment and there are extenuating circumstances (i.e., participant does not regularly receive transfusions at the site), then the RA may ask the participant to complete the questionnaire in clinic before his/her planned index transfusion.

Post-Transfusion

6. On the day of transfusion, the site RA will collect the completed pre-transfusion QUALMS survey. Study participants will then receive a second paper copy of the QUALMS, along with a stamped envelope addressed to the appropriate site.

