7. Participants will be instructed to complete this survey exactly one week after transfusion and return it using the pre-addressed, pre-stamped envelope.
8. Site RAs will call participants using script (see Appendix D) to remind them to complete the QUALMS survey exactly one week after transfusion.
 - The window may increase up to one extra week to accommodate for circumstances where the patient is unable to complete the post-transfusion QUALMS (i.e., participant does not feel well or participant forgot).

PTQA Report

9. Once received, the second assessment will be scored and compared with the first, and both the patient and provider will be sent a report with the results. The QUALMS validation study suggested that a clinically meaningful difference on the instrument is between 5 and 10 points;¹² For this study:
 - A post-transfusion score that is within 5 points of the pre-transfusion score will indicate a stable QOL
 - A post-transfusion score that increases by 5 or more points will indicate a clinically significant improvement in QOL
 - A post-transfusion score that decreases by 5 or more points will indicate a clinically significant decline in QOL
10. In our report, we will include language that encourages patient and providers to use these results to inform their next transfusion decision, specifically suggesting that transfusion be halted or decreased in frequency if QOL has worsened.

**PROTOCOL TITLE: A New Paradigm of Transfusion Decision Support for Patients with MDS:
Using Peri-Transfusion Quality of Life Assessments (PTQAs)**

Secondary Outcomes Assessment

11. At 8 weeks post-transfusion, all participants will be sent a survey (Appendix B) to assess the utilization of the PTQA and patients' decisional regret, perceptions of care, and perceived stress.

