11.0 Data Management and Confidentiality

11.1 Data Analysis Plan

Feasibility

Feasibility will be characterized by calculating (1) the proportion of enrolled patients out of all patients approached, and (2) the proportion of patients who completed both the pre- and post-transfusion QUALMS surveys out of all enrolled patients. A convenience sample of 60 evaluable patients will be enrolled to the study. To reach this goal, we will enroll 90 participants total, with the expectation that some patients will not be able to complete the study protocol, despite being eligible at the time of consent (e.g., do not end up requiring future transfusions). If the observed survey completion rate is 50% (i.e. 30/60), then this observed rate is consistent, with 95% confidence, with the true survey completion rate being as low as 38% or as high as 62%.

Clinical and Utilization Outcomes

To be assessed for clinical and utilization outcomes, participants must have completed a pre-transfusion QUALMS, received an index transfusion, and completed a post-transfusion QUALMS. Each of the 60 enrolled evaluable patients will be matched 1:1 to historical controls seen between 2015 and 2017, for a matched sample size of 120 patients total. Subjects will be matched for transfusion group, IPSS-R, pre-transfusion Hb, and institution). Comparative analyses will be conducted separately by transfusion group. For the transfusion-naive, the primary outcome will be receipt of second transfusion (yes/no) within two months following the first transfusion. For the transfusion-dependent, the primary outcome will be defined as number of units pRBCs received within two months following the next transfusion.

For both groups, we will also compare the number of hospitalizations and clinic visits two months after index transfusion (Table).

PTQA Utilization and Patient-Reported Outcomes

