11.4 Quality Control of Data

We will make every effort to collect all QUALMS data from study participants. RAs will call participants to remind them to complete the questionnaire and to either bring it with them to clinic (pre-transfusion) or mail it back to the site (post-transfusion). We have piloted this technique with 3 patients with MDS at DFCI; all complied. If a QUALMS survey is not complete, the site PI will personally contact each participant. Participants that do not complete the pre-transfusion QUALMS despite personal contact by the PI will be regarded as not having enrolled. We will record all reasons for non-enrollment, and account for all approached participants in the reports.

There may be participants who enroll and complete the pre-transfusion QUALMS, but do not complete the post-transfusion QUALMS. In this case, a PTQA report will not be generated. We will attempt to replace participants who do not complete the post-transfusion questionnaire, although this may prove unfeasible during the two-year timeframe of the study. Whether these participants are replaced or not, we will evaluate the outcomes of these participants, as we may find that there is a change in future transfusion decisions simply from drawing attention to QOL through the pre-transfusion QUALMS. If appropriate, sensitivity analyses will be performed among the subset of patients for whom a PTQA report was generated.

It is possible, although rare, for a patient to die within the two-month follow up period; such patients will be included in analyses based on their clinical and utilization outcomes observed before death.

We will record the number of patients who do not complete the two-month follow up surveys (PTQA utilization, decisional regret, perceptions of care, and perceived stress), and compare patient characteristics between those who do and do not complete the two-month follow up surveys.

**PROTOCOL TITLE: A New Paradigm of Transfusion Decision Support for Patients with MDS:
Using Peri-Transfusion Quality of Life Assessments (PTQAs)**

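### The Aim 1 completion rate is an eventual per-participant rate with a shrinking denominator, so it may exceed the feasibility of a single planned PTQA

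*Protocol*

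**What the plan says.** Section 1.1 (Aim 1) and section 11.1 agree on the measure. It is counted per participant: "the proportion of patients who completed both the pre- and post-transfusion QUALMS surveys out of all enrolled patients".

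Section 9.2 identifies the index transfusion by its success: "Index transfusion is defined as any upcoming transfusion appointment for which the participant has completed both the pre- and post-transfusion QUALMS questionnaires". If the pre-survey is missed for any reason, "then the RA may ask the participant to complete the questionnaire at home prior to a subsequent transfusion appointment", and "This subsequent transfusion will become the index transfusion". No number of attempts is stated. In extenuating circumstances, such as a participant who is not regularly transfused at the site, "then the RA may ask the participant to complete the questionnaire in clinic before his/her planned index transfusion". The post-survey has no such second chance at another transfusion. It has only a longer return period: "The window may increase up to one extra week".

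Section 11.4 adds "If a QUALMS survey is not complete, the site PI will personally contact each participant" and then "Participants that do not complete the pre-transfusion QUALMS despite personal contact by the PI will be regarded as not having enrolled". It also promises to record reasons for non-enrolment and to account for everyone approached.

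Sections 9.1 and Appendix F describe the assessment around one occasion, the patient's first or next transfusion. The data list in section 9.4 contains no attempt number, missed occasion or PI contact.

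**The concern.** A clinic considering PTQA would want to know how often one planned assessment succeeds. The planned rate answers a different question: how many participants get there in the end, after reminders, possible rescheduling to another transfusion and a call from the PI. A participant who failed at the first transfusion and succeeded at the second counts the same as one who succeeded at once, and nothing in the listed data separates them.

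Two features push the rate upwards. Retries add to the numerator. The rule in section 11.4 then removes from the denominator those who never return the pre-survey, although section 11.1 says the denominator is all enrolled patients. That rule moves the same people from a completion failure to an enrolment failure. The completion rate rises and the enrolment yield falls.

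The rate may also depend on how often a patient is transfused and on how readily each of the three sites uses its discretion to retry.

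**Working it through.** **The plan's own figure.** Section 11.1 gives 38% to 62% as the 95% interval for 30/60. The Wilson score interval is 37.7% to 62.3%, which reproduces it. No stated figure is wrong.

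**Inputs.** From the protocol: the per-participant rate (11.1), retry for the pre-survey only (9.2), removal of persistent pre-survey non-completers (11.4), 90 enrolled for 60 evaluable (4.1), and about 10 weeks on study including 8 weeks after transfusion (7.1). Not in the protocol, so assumed:
- q, pre-survey completion per opportunity: 0.5 to 0.8
- r, post-survey completion given a completed pre-survey: 0.8 to 1.0
- k, number of opportunities: 1 to 4

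**Numerator effect.** Only the pre-survey can be re-attempted, so with independent opportunities

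rate after k opportunities = r × (1 − (1 − q)^k).

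One retry (k = 1 to k = 2) adds r × q × (1 − q):

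| q | r = 0.8 | r = 1.0 |
|---|---|---|
| 0.5 | 40% to 60% (+20.0 points) | 50% to 75% (+25.0) |
| 0.8 | 64% to 76.8% (+12.8) | 80% to 96% (+16.0) |

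The gain over the assumed ranges is therefore about 13 to 25 points. In a middle example, q = 0.625 and r = 0.8, the rate is 50% at one opportunity, 69% at two, 76% at three and 78% at four. It can never exceed r = 80%.

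**If misses cluster.** When q varies between patients, the gain from one retry is r × (mean q × (1 − mean q) − variance of q). It is smaller than the figures above by r × the variance, and falls to zero if each patient either always or never completes. It cannot be negative.

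**How many retries fit.** 10 − 8 = about 2 weeks from consent to index. Section 11.2 assumes 8.0 units over the outcome period for dependent controls. At an assumed 1 to 2 units per visit that is 4 to 8 visits in 8 weeks, or one every 1 to 2 weeks. About one retry fits, if section 7.1 is read as a limit.

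**Denominator effect.** If 60 of 90 consented participants complete both surveys, the rate over everyone consented is 60/90 = 67%. If 10, 15 or 20 of the other 30 are reclassified as not enrolled, it becomes 60/80 = 75%, 60/75 = 80% or 60/70 = 86%. If every pre-survey non-completer is removed, the ratio is r × (1 − (1 − q)^k) / (1 − (1 − q)^k) = r. The rate then measures only post-survey completion among those who did the pre-survey, however many attempts that took.

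**Transfusion frequency, illustration only.** With q = 0.625, r = 0.8 and equal groups, three opportunities for dependent patients and one for naive patients give 76% against 50%. Dependent patients would then be 0.758 / (0.758 + 0.500) = 60% of completers.

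**The case against.** The strongest reply is that nothing is misstated. Sections 1.1 and 11.1 define the rate identically, neither calls it a first-attempt rate, and reminders, rescheduling and PI contact are described openly. The rate can be read as feasibility of PTQA as delivered, and no go/no-go threshold rests on it. This stands, and it makes the point one of interpretation and reporting. It does not answer the denominator rule in section 11.4, which sits badly with section 11.1. Nor does it supply attempt data, which are hard to recover if not recorded at the time.

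Three stronger readings are tempting and go too far.

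- A reader might infer unlimited automatic retries. Section 9.2 says the research assistant may ask, and section 7.1 leaves only about two weeks before the index. That duration is approximate and is not written as a cap, so it bounds the retries only loosely.
- A reader might apply 1 − (1 − p)^k to both surveys together and conclude that 60% becomes 84% and 94%, with an interval at first attempt that does not overlap the later ones. That requires r at or near 1. With q = 0.75 and r = 0.8 the same 60% becomes 75% and 79%. At n = 90 the Wilson intervals are 49.7% to 69.5% (54/90), 65.8% to 83.3% (68/90) and 69.4% to 86.0% (71/90), so both later ones overlap the first. The participants are the same people throughout, so comparing separate intervals is not a valid test anyway. Patients who never need another transfusion, a loss that section 4.1 expects, cannot be gained by any retry.
- A reader might infer that the rate is shown to favour frequently transfused patients. It may, but the in-clinic fallback in section 9.2 is aimed at those not regularly transfused at the site and partly offsets it. Section 11.2 also assumes that all naive controls receive a second transfusion, so the plan does not treat naive patients as lacking a second opportunity.

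**Conclusion.** The concern holds as a limit on what the Aim 1 rate can show. Over a common denominator, an eventual rate cannot be below the single-occasion rate. The rule in section 11.4 can only raise it further by removing failures. The direction is certain and the size is not derivable from the documents. About 13 to 25 points for one retry rests on q = 0.5 to 0.8, r = 0.8 to 1.0 and independent attempts, and clustering of misses makes it smaller. Dependence on transfusion frequency and site practice is plausible but unproven. The eventual rate is a legitimate measure that need not be replaced. It needs a companion figure and a stable denominator. This is a cheap improvement, not the correction of a false number.

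**What to change.** Keep re-indexing as the route to 60 evaluable participants, and keep the eventual completion rate. Add to section 11.1:

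- completion of both surveys around the first transfusion after consent, by transfusion group
- all consented participants in the denominator of both rates, with section 11.4 reworded so that persistent pre-survey non-completers count as non-completers and not as never enrolled
- separate lines for number of attempts, in-clinic completions and completions reached only after PI contact

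This needs a few REDCap fields: attempt number, place of completion and PI contact. The price is that the first-opportunity figure will look less favourable than the eventual one, and participants who never receive another transfusion will weigh on both. Their number should be shown so that the two kinds of loss can be told apart.

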9.3 Study Risks

As this is a survey study, we do not anticipate any risks due to study participation. The QUALMS survey (see Appendix A) has been extensively vetted to be acceptable to patients during its development and validation phases.¹³ Nevertheless, the PIs will be available for consultation if the survey questions make any participant upset and referral to appropriate resources (e.g., social work, counseling) will be made available. In the unlikely event that a patient is made upset or uncomfortable by the QUALMS survey, the study investigators will contact the treating physician to inform him or her of the patient's concerns.

9.4 Data Collection

Data will be collected via medical record reviews, the QUALMS, and several other survey instruments.

Primary medical record review will include:

- Sociodemographic information
- Information regarding patients' MDS diagnosis, including IPSS-R score
- The number/frequency of transfusions prior to index transfusion (for transfusion-dependent patients)
- Hemoglobin level prior to index transfusion

Secondary medical record review will include:

- The presence of a second transfusion since index transfusion (for those who are starting transfusion)
- The number of red cell units used since index transfusion (for those who are transfusion-dependent)
- The number of hospitalizations since index transfusion
- The number of clinic visits since index transfusion

Survey instruments will include:

- The QUALMS to assess pre- and post-transfusion MDS-related QOL (see Appendix A)
- The Decision Regret Scale, "About Your Care" domain of prior DFCI survey, and the PSS-4 to assess secondary outcomes related to decisional regret, perception of care, and perceived stress (see Appendix B)

10.0 Data and Specimen Banking

10.1 Data Storage

All data will be entered into a password-protected RedCap database, with hard copies

PROTOCOL TITLE: A New Paradigm of Transfusion Decision Support for Patients with MDS: Using Peri-Transfusion Quality of Life Assessments (PTQAs)

stored in locked file cabinets. We will not bank data for future use after study completion. This study does not involve specimen banking.

10.2 NA

10.3 NA

11.0 Data Management and Confidentiality

11.1 Data Analysis Plan

Feasibility

Feasibility will be characterized by calculating (1) the proportion of enrolled patients out of all patients approached, and (2) the proportion of patients who completed both the pre- and post-transfusion QUALMS surveys out of all enrolled patients. A convenience sample of 60 evaluable patients will be enrolled to the study. To reach this goal, we will enroll 90 participants total, with the expectation that some patients will not be able to complete the study protocol, despite being eligible at the time of consent (e.g., do not end up requiring future transfusions). If the observed survey completion rate is 50% (i.e. 30/60), then this observed rate is consistent, with 95% confidence, with the true survey completion rate being as low as 38% or as high as 62%.

Clinical and Utilization Outcomes

To be assessed for clinical and utilization outcomes, participants must have completed a pre-transfusion QUALMS, received an index transfusion, and completed a post-transfusion QUALMS. Each of the 60 enrolled evaluable patients will be matched 1:1 to historical controls seen between 2015 and 2017, for a matched sample size of 120 patients total. Subjects will be matched for transfusion group, IPSS-R, pre-transfusion Hb, and institution). Comparative analyses will be conducted separately by transfusion group. For the transfusion-naive, the primary outcome will be receipt of second transfusion (yes/no) within two months following the first transfusion. For the transfusion-dependent, the primary outcome will be defined as number of units pRBCs received within two months following the next transfusion.

For both groups, we will also compare the number of hospitalizations and clinic visits two months after index transfusion (Table).

PTQA Utilization and Patient-Reported Outcomes

We may find that patients and hematologists do not use the information in their PTQA reports to truly affect decision-making, as both may be anxious to forgo transfusions despite the fact that QOL did not improve. We plan to assess this parameter at two months post-transfusion by asking participants whether they discussed the PTQA report with their physician (see Appendix B). To help prevent the PTQA going unused, we will make sure that providers at each site have access to the consensus Hb data from our previous qualitative study (Protocol 18-064). These results will be disseminated to providers prior to study initiation. In addition, we will work closely with the DFCI Adult Patient and Family Advisory Council (PFAC) to vet the routine language in our PTQA patient reports so that is optimally educational and anxiety-reducing.

PROTOCOL TITLE: A New Paradigm of Transfusion Decision Support for Patients with MDS: Using Peri-Transfusion Quality of Life Assessments (PTQAs)

Exploratory analyses (e.g. descriptive statistics such as means and standard deviations) using the results from the follow-up survey (see Appendix B) will characterize decisional regret, perceptions of care, and perceived stress by the associated scales at two months post-transfusion (Table).

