1.0 Objectives

1.1 Study Aims

The goal of this multi-center study is to determine how to tailor blood transfusion decisions to the quality of life (QOL) changes experienced by individual patients with myelodysplastic syndromes (MDS). We will assess this by piloting a peri-transfusion QOL assessment (PTQA) approach. The PTQA involves administering a QOL questionnaire (see Appendix A) to study participants before and after an upcoming transfusion appointment and comparing QOL scores.

Specific Aim 1

Assess the feasibility of PTQA. We will assess the feasibility of this new paradigm of decision support by determining the enrollment yield as a percentage of all patients approached. We will also assess feasibility by calculating the proportion of enrolled participants who complete both the pre- and post-transfusion the Quality of Life in Myelodysplasia Scale (QUALMS).

Specific Aim 2

Assess the potential usefulness of PTQA in improving clinical and utilization outcomes. We will use medical record review and match our participants to historical controls (matched for transfusion group; IPSS-R; pre-transfusion Hb; and institution) to assess our primary outcomes, which are:

1. The presence of second transfusion after PTQA (for transfusion-naive)
2. The number of red cell units used after PTQA (for transfusion-dependent)
3. The number of hospitalizations after PTQA (for both transfusion groups)
4. The number of clinic visits after PTQA (for both transfusion groups)

Specific Aim 3

Explore the potential impact of PTQA on patient-reported outcomes. At 8 weeks post-transfusion, we will send participants a follow-up questionnaire (see Appendix B) to assess the following secondary outcomes:

1. PTQA utilization
2. Decisional regret
3. Perception of care
4. Perceived stress

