4.0 Study-Wide Number of Subjects

4.1 Accrual Goal

Our study-wide accrual goal is 60 evaluable participants. To reach this accrual goal, we will consent and enroll 90 participants as some participants are not able to complete the protocol due to a variety of reasons (e.g., participant does not end up requiring future transfusions). The 60 evaluable participants will be matched 1:1 to historical controls seen between 2015 and 2017, for a total sample size of 120.

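### The Aim 1 survey completion rate has no single sound denominator: all enrolled, the evaluable target of 60, and a rule that un-enrols pre-survey non-responders give different answers

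*Protocol*

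**What the plan says.** Protocol section 1.1 (Specific Aim 1) assesses feasibility by "calculating the proportion of enrolled participants who complete both the pre- and post-transfusion" QUALMS. Section 11.1 repeats this as "the proportion of patients who completed both the pre- and post-transfusion QUALMS surveys out of all enrolled patients".

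The planned numbers are in sections 4.1 and 11.1: "Our study-wide accrual goal is 60 evaluable participants", and "To reach this goal, we will enroll 90 participants total". Section 4.1 explains the surplus by saying that "some participants are not able to complete the protocol due to a variety of reasons (e.g., participant does not end up requiring future transfusions"). Section 11.1 gives the same example.

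Section 11.1 then illustrates precision: "If the observed survey completion rate is 50% (i.e. 30/60"), the result is compatible with "the true survey completion rate being as low as 38% or as high as 62" per cent. For the clinical and utilization analysis, the same section says that "participants must have completed a pre-transfusion QUALMS, received an index transfusion, and completed a post-transfusion QUALMS", and it refers to the 60 evaluable patients as the ones entering that analysis.

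Two procedural sections bear on the denominator. Section 9.2 times the pre-transfusion survey to the day before a transfusion and the post-transfusion survey to one week after it. Section 11.4 states that a participant who still has no pre-transfusion QUALMS after contact from the site investigator counts as never having enrolled.

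**The concern.** Both surveys are tied to a transfusion. A patient who consents and is never transfused cannot complete the pair, however willing. The protocol expects some such patients, yet it calls completers over all enrolled the survey completion rate. A low value could mean that transfused patients do not return questionnaires, or that patients were enrolled who turned out not to need blood. The first concerns the assessment itself; the second concerns how early patients are identified.

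The other two statements pull elsewhere. The 30/60 example uses a denominator in which, by the protocol's own use of evaluable, everyone is a completer. The section 11.4 rule takes out patients who had the chance to complete the pre-survey and did not, which are failures that a feasibility measure should count. It also moves them from enrolled to non-enrolled in the other Aim 1 measure, the enrolment yield.

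Survey completion is one of only two Aim 1 measures. Two analysts following the text could report materially different rates from the same data.

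**Working it through.** **Inputs.** Planned enrolment 90 and evaluable target 60 (sections 4.1 and 11.1); precision example 30/60 with an interval of 38% to 62% (section 11.1). The protocol does not say how the 30 non-evaluable patients divide, so the splits below are assumptions.

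**1. The plan's own interval.** Wilson score interval, z = 1.96, p = 0.5:

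- Half-width = z·√(p(1−p)/n + z²/4n²) / (1 + z²/n); with p = 0.5 the centre is 0.5.
- n = 60: 1.96·√(0.25/60 + 3.8416/14,400) / (1 + 3.8416/60) = 0.123, giving 37.7% to 62.3%.

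This rounds to the stated 38% to 62%, so the arithmetic is right for 30/60. (The Wald and Clopper-Pearson intervals round to 37% to 63%.)

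**2. Is 60 the right denominator?** If 60 means evaluable patients, the rate is 60/60 = 100% by definition and 30/60 cannot occur. If the denominator is the 90 enrolled, a 50% rate is 45/90, with half-width 1.96·√(0.25/90 + 3.8416/32,400) / (1 + 3.8416/90) = 0.101, giving 39.9% to 60.1%. Thirty completers would be 30/90 = 33.3% (Wilson 24.4% to 43.6%).

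**3. All enrolled against transfused only.** Let k be the number enrolled but never transfused, with 60 completers. The reported rate is 60/90 = 66.7%, and the rate among transfused patients is 60/(90 − k). The relative understatement is 1 − (60/90)/(60/(90 − k)) = k/90.

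| k (assumed) | Transfused-only rate | Gap in points | Relative understatement |
|---|---|---|---|
| 0 | 60/90 = 66.7% | 0 | 0% |
| 10 | 60/80 = 75.0% | 8.3 | 11% |
| 15 | 60/75 = 80.0% | 13.3 | 17% |
| 20 | 60/70 = 85.7% | 19.0 | 22% |
| 30 | 60/60 = 100% | 33.3 | 33% |

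**4. The section 11.4 rule.** Split the 30 into k never transfused, a transfused without a pre-survey, and b transfused with a pre-survey but no post-survey. Assume that never-transfused patients have no pre-survey. Take k = 20, a = 5, b = 5:

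- All enrolled: 60/90 = 66.7%.
- Rule applied to everyone without a pre-survey: 60/(90 − 20 − 5) = 60/65 = 92.3%.
- Rule applied only to transfused patients without a pre-survey: 60/(90 − 5) = 60/85 = 70.6%.
- Transfused patients, with both kinds of survey failure kept: 60/(90 − 20) = 60/70 = 85.7%.

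Here the rule in its wider reading overstates completion by 6.6 points. At the extreme k = 0, a = 30, b = 0, it gives 60/60 = 100%, although only 60/90 = 66.7% of transfused patients completed both surveys.

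**The case against.** The strongest defence is that completers over all enrolled is a legitimate feasibility measure. Aim 1 concerns the whole approach, including finding patients who are heading for transfusion, and enrolling patients who never reach one is itself a feasibility result. The protocol attaches no threshold to the rate, so no decision turns on it. This stands: the all-enrolled figure should be kept as the overall yield. What it cannot do is separate the two causes of a low value.

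The 30/60 example can also be defended as a rough illustration of precision. That is fair as to its size, since 45/90 gives a similar interval, but it leaves the denominator unclear.

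A reader might infer that the protocol understates completion by a third. The documents do not support that. One third requires all 30 non-evaluable patients to be never transfused, whereas section 4.1 speaks of a variety of reasons and offers lack of need for transfusion only as an example. Sections 9.2, 11.4 and 13 show other routes, such as forgotten surveys, missing post-surveys and withdrawal. Section 3.2 also excludes patients with no plans for potential outpatient transfusion, and section 22.1 approaches those nearing first transfusion at the appointment before it. Read literally, section 11.4 may remove many never-transfused patients from the denominator, so the error need not be an understatement at all.

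A reader might also infer that the loss falls mainly on the transfusion-naive group. That is plausible, because the other group enters with transfusions already scheduled, but no section gives loss by group.

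Finally, section 11.4 does promise to record reasons for non-enrolment and account for everyone approached. The information is therefore not lost; it is placed outside the completion rate.

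**Conclusion.** The point holds as a conflict of denominators. Sections 1.1 and 11.1, the 30/60 example and the section 11.4 rule cannot all describe one rate, and none yields completion among patients who had the opportunity to complete. With the planned 60 of 90, the all-enrolled rate falls short of the transfused-only rate by anything from nothing to 33.3 points. Under section 11.4 the error can run the other way. Both directions rest on assumed splits of the 30 non-evaluable patients, so neither the sign nor the size can be fixed from the protocol. The stated interval is correct for 30/60; the fault is in what the 60 stands for. The consequence is limited to how Aim 1 is interpreted, since no success criterion depends on it.

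**What to change.** Amend sections 1.1, 11.1 and 11.4 together; changing only the first two would leave a contradiction with the third.

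- Count every consented participant as enrolled for Aim 1. Delete the rule that un-enrols patients without a pre-transfusion QUALMS, or limit it to purposes other than Aim 1.
- Report completers of both surveys over all enrolled, and call it the overall yield.
- Report separately, by transfusion group, (i) the proportion of enrolled patients who received any red cell transfusion after consent during participation, and (ii) the completion rate among those transfused, keeping patients who missed either survey in the denominator. The two multiply to the yield: with k = 20, 70/90 × 60/70 = 60/90.
- Restate the precision example on the denominator used, for instance 45/90 = 50% with a Wilson 95% interval of about 40% to 60%.

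The cost is a few sentences and one added record-review item. Section 9.4 lists transfusions only relative to the index transfusion, and section 9.2 defines an index transfusion as one with both surveys completed. Transfusions in non-completers are therefore not yet a listed item. The transfused-only rate has a smaller denominator and so a somewhat wider interval at any given rate: at 50%, 37.7% to 62.3% with 60 transfused against 39.9% to 60.1% with 90. Rates by transfusion group will be less precise still. Survey procedures and sample size do not change.
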